	
the imaging schedule may be modified based on the imaging data from the first cohort of patients.
 
The optimal time point for PET scanning will be determined based on the analysis of the tumor to background ratio and tumor to blood pool ratio at different timepoints. Tumor to background ratio is defined as the ratio between tumor tracer uptake and the radioactivity on the opposite site or gluteus maximus, etc. The first PET scan will be performed in combination with a low-dose CT scan for attenuation correction and anatomic reference. An independent radiology review committee (IRC), consisting of principal investigator and nuclear medicine physicians, will be established to evaluate all imaging data.
 
If there is no radioactivity or a small amount of radioactivity in the target lesion as evaluated by the IRC, and the safety criteria are met, the dose will be escalated per the escalation guidelines. If the tumor to background ratio is high per the IRC, three patients will be enrolled at the next higher level and the IRC will determine whether dose escalation should stop based on the imaging data from these three patients. Blood samples will be collected from a peripheral vein to evaluate ADA, PK and the radioactivity in the circulation.
 
 • The time points for blood sample collection are as follows: within 30 minutes before injection of SNA002, at 2 ± 1 minutes, 5 ± 1 minutes, 10 ± 1 minutes, 30 ± 2 minutes, 50 ± 5 minutes, 100 ± 5 minutes and 150 ± 10 minutes post injection. All blood samples are sent to the central laboratory for PK analysis. Radioactivity in the blood sample (whole blood and serum) will be obtained using a γ-well-type detector and measured activity concentrations will be converted to percentage injected activity/L. • Urine sample will be collected to evaluate the renal excretion of radioactivity before injection, at 90 ± 30 minutes, 180 ± 30 minutes and 300 ± 30 minutes post injection. Counts in aliquots of serum or urine will be obtained using a γ-well-type detector and measured activity concentrations will be converted to percentage injected activity/L. 
Blood samples will be taken 30 minutes before administration, on $D6\pm 1$d and $D28\pm 2$d, and will be sent to the central laboratory for ADA analysis. Patients were discharged from the study after blood samples were collected on $D28\pm 2$d. Following the last PET scan, tumor biopsies or operation (if surgery is available) will be obtained. The investigator will determine the number and location of lesions for biopsy for each patient in consultation with the surgeon or interventional radiologist; these should be easily accessible and have positive or negative tracer uptake. Biopsy sites should not exceed 5 for each patient and ideally include both negative lesions and positive lesions. If taken an operation on tumor, the IRC will observe IHC result of tumor and PET scan.
 
The study will be end for patient after completing blood collection on $D28\pm 2$d.
 
Region-of-Interest Definition
 
Regions of interest (ROIs) will be used to determined SNA002 uptake in different organs. Organs with tracer uptake will be drawn using PMOD software based on the PET image, including all activities on the PET images that are contributing to the organ. For organs without tracer uptake, organ delineation will be based on CT data.
 
To calculate the biodistribution and dosimetry in normal organs with tracer uptake, a semiautomatic (region grow) method will be used to delineate the ROI on the PET images. For normal organs without tracer uptake, the ROI will be delineated based on CT scan.
 
Dosimetry
 
Time-activity curves were derived from volumes of interest for each source organ (i.e., brain, heart, lungs, liver, spleen, kidneys, and thyroid) delineated on the whole-body images using PMOD.
 
To define volumes of interest (VOIs) the dynamic study was loaded with all or some frames averaged, depending on the evaluated organ. VOIs were defined manually for heart, liver, gallbladder, kidneys with all frames averaged.
 
Using the PMOD software the VOIs consisted of regions of interest (ROIs) which were defined at the outer contour of the organ. In this way (decay-corrected) TACs of the organs' average radioactivity concentrations and their volumes were obtained.
 
An example, FYI: Source Organs: For dosimetric calculations, the following source organs were included: kidneys, red marrow, cortical bone mineral surface, trabecular bone mineral surface, urinary bladder content, and remainder body. Red marrow activity uptake was estimated from venous blood sampling.
				

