5.1 Inclusion criteria

Patients must meet all the following criteria to be eligible for participation in this study:

- 1) Male or female patients, 18-75 years of age, inclusive.
- 2) Willing and able to provide signed and dated informed consent prior to any study-related procedures and willing and able to comply with all study procedures.

- 3) Histologically or cytologically confirmed solid tumors including but not limited to non-small cell lung cancer, breast cancer, esophageal cancer, head and neck carcinoma, ovary cancer and melanoma (with or without metastasis); Patients are allowed to enter the study at first diagnosis, at relapse or under treatment.
- 4) Obtain pathological results within one year.
- 5) Patients with the imaging results showing at least 1 tumor lesion that can be sampled by biopsy (enhanced CT, enhanced MRI or ^{18}F -FDG PET/CT results are acceptable).
- 6) ECOG PS 0-2 (See [Appendix 1](#) for details).
- 7) Adequate hepatic function as evidenced by meeting all the following requirements:
 - a) Total bilirubin (TBIL) $\leq 2.5 \times \text{ULN}$.
 - b) Aspartate aminotransferase (AST) and alanine aminotransferase (ALT) $\leq 3 \times \text{ULN}$.
- 8) Serum creatinine $< 1.5 \times \text{ULN}$ and blood urea nitrogen (BUN) $\leq 1.5 \times \text{ULN}$.
- 9) Adequate hematological function defined as:
 - a) White blood cell $3.0-10.0 \times 10^9/\text{L}$ in prior to study entry
 - b) Absolute neutrophil count $1.5-7.0 \times 10^9/\text{L}$ without growth factor support in prior to study entry
 - c) Hemoglobin $\geq 90\text{g/L}$ without transfusion in prior to study entry
 - d) Platelet count $75-300 \times 10^9/\text{L}$ without transfusion in prior to study entry
- 10) Coagulation tests, defined by the following:
 - a) Activated partial thromboplastin time (PTT) $\leq 1.5 \times \text{ULN}$
 - b) International normalized ratio (INR) $\leq 1.5 \times \text{ULN}$.
- 11) Blood pressure value $<$ grade 1 hypertension (including patients with a history of hypertension whose systolic blood pressure is $< 140 \text{ mmHg}$ and diastolic blood pressure is $< 90 \text{ mmHg}$ after exercise or drug treatment).
- 12) Baseline heart rate 60-100/minute (inclusive)

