6.1.7.2 Dose Escalation Schedule

The dose escalation is determined through both imaging results and safety results:

Imaging:

The Imaging Reviewer Committee consisted of the principal investigator and nuclear medicine physicians.

- 1) If the first three positive tumor lesions in a certain dose group judged by the IRC having a high image quality (such as $\text{T}/\text{B} > 1.5$, etc.), it can be decided from the imaging perspective to increase to the next dose group after continuing to enroll 3-4 cases in this dose group, or directly increase to the next dose group for further exploration;
→If the quality of the first 3 cases in the subsequent dose group is comparable to that in the previous dose group, the IRC shall discuss whether to discontinue further enrollment from a

imaging perspective (e.g. The image quality of the first 3 cases in the 0.3mg dose group is similar to that in the 0.1mg dose group, then stop recruiting, and the 0.1mg dose was identified as the optimal image dose).

- If the quality of the first 3 cases in the posterior dose group is higher than prior, another 3 to 4 cases will be enrolled. After the completion of the posterior dose group, the IRC will discuss and decide whether this group should not be explored from the imaging aspect (e.g. The image quality of the first 3 cases in the 0.3mg dose group is higher than that in the 0.1mg dose group, then 3-4 cases , and the subsequent dose exploration was not carried out, and the 0.3mg dose was identified as the optimal image dose).

- 2) If the first three positive tumor lesions in a certain dose group judged by IRC present poor imaging quality (such as $T/B \leq 1$) or nonvisualization (functional imaging without nuclides), the decision of stopping enroll in this dose group can be made from an imaging perspective, and the dose group can directly increase to the next or second dose group (for example, if the imaging quality of the 0.1mg dose group is poor in three consecutive cases, the dose group can increase to the 0.3mg or 0.5mg dose group);
- 3) If the last dose group shows nonvisualization of the positive tumor lesions determined by the IRC in the first three cases, discussion will be conducted to determine whether to adjust the subsequent dose from the imaging perspective or terminate the entire clinical trial.

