- 4) After the dose escalation of all dose groups is completed, the imaging expert committee and the principal investigator will decide whether to continue enrolling 3-4 subjects in a certain initially identified optimal dose group for further exploration.

Security:

The principal investigator determines whether to increase the dose from the perspective of safety. Dose escalation should be stopped if one of the principles happen:① at least half of subjects in a dose group experience CTCAE grade 2 (or moderate) or above adverse reactions;② or at least 1/3 subjects experience CTCAE grade 3 (or severe) or above adverse reactions;③ or one serious adverse reaction in certain group.

The dose escalation will be determined by the principal investigator based on both imaging and safety results. During the clinical trial, based on the principle of subject protection, the dose group can be rapidly escalated to the subsequent dose group if nonvisualization or the above safety events happens after only one subject enrolled according to the investigator's discretion.

[figure not shown]

Figure 3 Dose escalation

After the dose escalation of all dose groups is completed, the imaging expert committee and the principal investigator will decide whether to enroll another 3 or 4 patients in the identified optimal dose group.

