7.3 Study Schedule

7.3.1 Screening

D - 14 to D - 2

- Sign the ICF.
- PD-L1 immunohistochemistry results.
- Collect demographic data.

- 4) Inquire and record medical history (including personal history, past history, allergy history, and cancer history).
- 5) Tumor stage.
- 6) Pathological test results within 1 year before screening.
- 7) Vital signs.
- 8) Physical examination.
- 9) 12-lead ECG.
- 10) Cardiac function score: scored according to NYHA standards
- 11) ECOG score.
- 12) Chest x-ray (not required if chest CT results are available).
- 13) Enhanced CT/enhanced MRI/PET-CT (results of examinations conducted at the study site or other tertiary hospitals within 30 days prior to enrollment are acceptable).
- 14) Laboratory tests: blood routine, blood biochemistry, electrolyte, coagulation function, urine routine, serum virology, thyroid function tests, and serum pregnancy test (only for female subjects of childbearing age). Serum virology can accept results within 28 days before screening, while other laboratory tests can accept results within 7 days before screening.
- 15) Review compliance with inclusion/exclusion criteria.
- 16) Record concomitant medications.

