9. ADA: blood samples were collected within 30 minutes before administration, on D6 ± 1d and D28 ± 2d during the safe follow-up period. All blood samples were tested in an independent third-party central laboratory.
10. Systemic PET-CT: Three systemic PET CT scans are performed at 15±5 minutes, 60±10 minutes, and 120±20 minutes after administration. Panoramic PET-CT scans performed after dosing were acceptable for 1 to 2 subjects in a dose group or each dose group and were required to cover at least one of these time points.
11. Measurement of Radiation Dose: measure the surrounding radiation dose at 4 ± 0.5 hours after administration.
12. PD-L1 Immunohistochemical Examination and Formulate a Plan for Obtaining Target Lesion Specimens (If Performed) : Obtain the PD-L1 immunohistochemical results of the subjects at the study site during the screening period. This experiment determines whether to collect tissue specimens after administration based

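### The imaging text is inconsistent about which lesions inform the dose decision, so absent uptake in a PD-L1-negative lesion can be read as a failed mass dose

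*Combined protocol and SAP*

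**What the plan says.** **Entry.** Section 5.1 admits patients with "Histologically or cytologically confirmed solid tumors including but not limited to non-small cell lung cancer", and the lesion criterion is "Patients with the imaging results showing at least 1 tumor lesion that can be sampled by biopsy". No criterion in section 5.1 or 5.2 sets a PD-L1 level.

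**PD-L1 measurement.** Screening (section 7.3.1) lists "PD-L1 immunohistochemistry results", and a note to Table 4 (section 7.3.7) says "Obtain the PD-L1 immunohistochemical results of the subjects at the study site during the screening period". The Protocol Summary names the 22C3 assay for tissue taken on Day 2, gives no cut-off, and says that the imaging review committee (IRC) reviews IHC and its agreement with PET.

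**Imaging and dose.** The Study Design text of the Protocol Summary begins its escalation condition with "If there is no radioactivity or a small amount of radioactivity in the target lesion", leaves that judgement to the IRC, adds that safety criteria must be met, and refers on to the escalation guidelines. Those rules, in the Summary and in section 6.1.7.2, begin "If the first three positive tumor lesions in a certain dose group". A later provision in section 6.1.7.2 says "the dose group can be rapidly escalated to the subsequent dose group if nonvisualization or the above safety events happens after only one subject", at the investigator's discretion. Section 6.1.8 covers absent activity in lesions at 0.9 mg, and section 5.4 lists absence of imaging after dose adjustment as a ground for ending the trial.

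**Analysis.** Section 10.4.2 bases the optimal imaging time on the tumour-to-background ratio (T/B), and the optimal dose on T/B, lesion detection and a further condition on normal organs. Section 10.4.3 takes IHC as the truth, with post-administration IHC replacing baseline IHC where both exist, and computes sensitivity, specificity and predictive values.

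**The concern.** The tracer is intended to show PD-L1-positive lesions. In a PD-L1-negative lesion, no uptake is the correct result and says nothing about whether the protein mass was adequate. A dose decision drawn from imaging therefore needs to state which lesions count, and the text states it in several incompatible ways.

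Two things are at stake. First, a true negative may be taken as evidence that a dose level does not image; under rule 2 of section 6.1.7.2 this can close enrolment at that level. Second, dose levels are compared on the image quality of their first three cases. A difference in T/B or detection between two such cohorts may reflect how many patients in each had PD-L1-positive tumours, not the mass dose. Recommended diagnostic dose and optimal imaging window are secondary endpoints (section 4.2), so both problems reach the reported conclusions.

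**Working it through.** **Step 1. The provisions side by side.**

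| Place | What it acts on | PD-L1 condition |
|---|---|---|
| Protocol Summary, Study Design | Target lesion | None stated; refers to the guidelines |
| Rules 1 and 2 (Summary; 6.1.7.2) | First three 'positive' lesions | Term not defined |
| Sub-rules of rule 1; example in rule 2 | First three, or three consecutive, cases | None |
| Rule 3 | 'Positive' lesions not visualised in the last dose group | Term not defined |
| One-subject provision (Summary; 6.1.7.2) | One subject | None |
| 6.1.8 | Lesions at 0.9 mg | None |
| 5.4 | Imaging as a whole | None |

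**Step 2. What 'positive' could mean.** Elsewhere the protocol uses the word for PET uptake: the biopsy text of the Summary and of section 7.3.3 contrasts lesions that are positive and negative on the scan. In that sense a positive lesion that is not visualised, as in rules 2 and 3, contradicts itself. If it means IHC-positive, rules 1 to 3 are coherent, but the text never says so, gives no cut-off, and does not extend the condition to the other provisions. If any target lesion counts, true negatives count as poor imaging.

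**Step 3. Against the analysis section.** Under section 10.4.3, an IHC-negative lesion without uptake enters specificity and negative predictive value as a true negative. Under the unqualified provisions, the same lesion can stand as absent imaging at that dose.

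**Step 4. Illustration of size.** The plan's sample size reproduces: 4 levels × 3 = 12 and 4 × 7 = 28 (section 10.5). It is not based on a hypothesis test. The documents give no PD-L1 prevalence. Let q be the share of patients whose assessed lesion is negative, with q = 0.3, 0.5 and 0.7 as assumptions. Assume also one lesion per patient, independence, and no uptake in negative lesions.

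- All of the first three negative: q³.
- At least one of three negative: 1 − (1 − q)³.
- Two cohorts of three with different numbers of positives: 1 − Σ P(k)², where P(k) is the binomial probability of k positives in three. At q = 0.5: 1 − (1 + 9 + 9 + 1)/64 = 0.688. At q = 0.3 or 0.7: 1 − (0.343² + 0.441² + 0.189² + 0.027²) = 1 − 0.349 = 0.651.

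| q | All three negative | At least one negative | Two cohorts differ in mix |
|---|---|---|---|
| 0.3 | 2.7% | 65.7% | 65.1% |
| 0.5 | 12.5% | 87.5% | 68.8% |
| 0.7 | 34.3% | 97.3% | 65.1% |

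**Step 5. The one-subject provision.** Given that a subject's lesion is not visualised, the probability that it is negative is q / (q + (1 − q)m), where m is the chance that a positive lesion is missed. With m = 1 this equals q; with m = 0 it equals 1. Prevalence is therefore a lower bound on this probability.

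**The case against.** Much can be said for the plan. The Study Design text is a summary that leaves the assessment to the IRC and refers to the escalation guidelines, whose main rules do say 'positive'. The Summary places the 22C3 assay and the IRC's review of IHC directly before those rules, and the stated indication is PD-L1-positive lesions, so an IHC reading is the natural one. The decisions are permissive: the one-subject provision is discretionary, and rule 2 says what can be decided. Section 10.4.3 already classes an IHC-negative lesion without uptake correctly, and no text instructs anyone to tabulate it as imaging failure. The dose-escalation figure is not visible here and might clarify the term.

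These points narrow the concern but do not close it. Nothing visible makes IHC an input to the dose decision or says how IHC-negative or IHC-unknown lesions are handled. The guidelines themselves move from lesions to cases, and the one-subject provision beside them has no qualifier. Discretion over an undefined term does not make the dose conclusion reproducible.

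A reader might go further and infer that open entry is itself a fault. The documents do not support that: the exploratory objective on positive and negative predictive efficacy, and the plan to biopsy both kinds of lesion, need PD-L1-negative tumours. Nor do they support the inference that the protocol escalates automatically whatever the PD-L1 status, given the reference to the guidelines and the permissive wording.

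**Conclusion.** The point holds as an inconsistency that affects inference about dose. The passages differ on which lesions count, 'positive' is undefined, and the PET sense used elsewhere makes part of the rule self-contradictory. Absent uptake in a PD-L1-negative lesion can therefore be read as a failed mass dose, and the comparison of dose levels can be confounded by PD-L1 mix in very small cohorts.

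Its size cannot be fixed from the documents. The percentages in the working are illustrative and depend on the assumed prevalence and on one independent lesion per patient. The rules count lesions, several of which may come from one patient. The three-negative figure bears only on readings without an IHC condition, and the Study Design text states no count for low uptake. A reader might take an assumed 30% to 70% negative share as the most that a single non-visualised subject could be a true negative. That share is the floor, as step 5 shows.

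**What to change.** 1. Reconcile the Study Design text and dose-escalation rules of the Protocol Summary with sections 5.4, 6.1.7.2 and 6.1.8, so that all say which lesions the imaging judgement rests on. Define 'positive' once: assay, cut-off and specimen. How the dose decision is then made is for the sponsor; no dose or escalation rule is proposed here.

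2. In the optimal-dose and imaging-time analysis (section 10.4.2), report visualisation and T/B at each dose level by lesion IHC status: positive, negative or unknown. Use the order in section 10.4.3, post-administration IHC where available and otherwise baseline, and record specimen site and date. Screening IHC alone would conflict with that order. An IHC-negative lesion without uptake is then not counted as imaging failure.

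**Cost.** Protocol wording, a few data fields and extra table columns; the tabulation itself needs no additional patients. The strata will be small, and some lesions will have unknown or outdated IHC, since pathology up to one year old is accepted at entry and new tissue is not always taken. It should not be assumed that 3 to 7 patients always give three IHC-positive lesions. The chance that seven patients include at least three positives is 1 − Σ C(7,k)(1 − q)^k q^(7−k) over k = 0 to 2. That is 97.1%, 77.3% and 35.3% at q = 0.3, 0.5 and 0.7 (for q = 0.5, 1 − 29/128 = 0.773), under the same assumptions.

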Study Design	
Overall Study Design
 
This is an open-label, dose escalation study to evaluate the safety, PK, biodistribution, dosimetry, and tumor targeting potential of SNA002 in patients with solid tumors.
 
This study will consist of Screening Period, Baseline Period, Study Period and Safety Follow-up Period. A signed and dated informed consent form will be obtained before any study-related procedures are performed. Collect CT/MRI/PET/CT results from subjects within one month before screening to obtain baseline tumor assessment. Eligible patients will be enrolled at least two days before the administration of study drug. The radiation dose for all dose groups at the time of administration should be ranged from 37 to 200MBq. Four dose levels of NOTA-SNA002 are planned: 0.1mg, 0.3mg, 0.5mg and 0.9mg. The final drug product administered to the patient is [⁶⁸Ga]Ga-NOTA-SNA002. Three to seven patients will be sequentially enrolled into each dose cohort. Patients will be administered a single dose of SNA002 over 1 minute as an intravenous bolus. Patients will be observed for 6±1h and 24±6h post infusion for infusion-related and other adverse reactions. In the first cohort of patients, whole body imaging will be acquired using PET/CT at 15±5 minutes, 60±10 minutes and 120±20 minutes post-injection. Before each imaging, the patients need to empty bladder as much as possible. Total-body PET-CT scans can be performed on 1-2 subjects in a certain dose group or each dose group, covering at least one of the aforementioned time points. In the subsequent cohorts,

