6.1.7 Starting Dose and Dose Escalation Schedule

6.1.7.1 Starting Dose

SNA002 does not bind to mouse, rat and dog PD-L1. Therefore, cynomolgus monkey was chosen in biodistribution studies and repeat-dose general toxicity studies. ^{68}Ga -NOTA-SNA002 can specifically bind to PD-L1 proteins of primates, and the radioactivity uptake is low in other organs except for the excretion organs (kidneys and bladder). The estimated absorbed dose (effective dose) converted from cynomolgus monkeys to adult male or female is 0.022-0.023mSv/MBq, which shows good radiation safety. The recommended dose of ^{68}Ga -NOTA-SNA002 for clinical trials is 185 MBq (5mCi), which generates an effective dose of about 4.1 mSv indicating safe use of ^{68}Ga -NOTA-SNA002 for clinical diagnostics. A NOAEL approach based on the pivotal monkey 2-week study toxicity findings was used to determine the maximum recommended starting dose (MRSD) for the first in human study. In the 2-week monkey study, the potential infusion reaction is the only toxicity observed after 3 repeated iv doses. the dose of 1.5 mg/kg (mean $\text{AUC}_{0-t} = 20700 \text{ ng}\cdot\text{h}/\text{mL}$; mean $\text{C}_{\text{max}} = 32000 \text{ ng}/\text{mL}$) and 0.5mg/kg (mean $\text{AUC}_{0-t} = 5060 \text{ ng}\cdot\text{h}/\text{mL}$; mean $\text{C}_{\text{max}} = 10500 \text{ ng}/\text{mL}$) was considered the NOAEL for males and females, respectively. Since the molecular weight of ^{68}Ga -NOTA-SNA002 is less than 100KD, The HED is 0.48 mg/kg (male) and 0.16 mg/kg (female) based on body surface. The MRSD is considered to be 0.048 mg/kg (male) and 0.016 mg/kg (female) (1/10 of NOAEL). The highest dose that nonclinical can cover is considered to be 0.24 mg/kg (male) and 0.08 mg/kg (female) (1/2 of NOAEL). The proposed human dose ranges are from 0.00167 mg/kg (0.1mg flat dose) starting dose to the highest ascending dose 0.01503mg/kg (0.9mg flat dose). The starting dose is 28.74- and 9.58-fold lower than the MRSD for males and females, respectively. The highest ascending 0.01503 mg/kg is covered by nonclinical data ($\frac{1}{2}$ of the NOAEL). Therefore, the proposed clinical mass dose range of 0.00167mg/kg to 0.01503mg/kg is not expected to pose a significant risk to patient safety.

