7.2.2 Other Assays or Procedures

Anti-SNA002 antibody: Blood samples are collected within 30 min before drug administration and on D6±1d, D28±2d during the safety follow-up. All blood samples are tested in the central laboratory.

Radiation exposure of subjects: The radiation exposure is calculated using OLINDA software. Radioactivity uptake of each organ are input into EXM. Double exponential fitting is performed for each organ. Then OLINDA calculates the decomposition of the drug in each source organ and the radiation doses of all target organs. The organs covered in the fitting calculation include but are not confined to brain, chest, bladder, lungs, liver, kidneys, spleen, gastrointestinal tract, and thyroid glands.

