3. Laboratory examination: Subjects should obtain blood routine (red blood cell count, white blood cell count, hemoglobin, platelet count, neutrophil count, lymphocyte count, monocyte count), blood biochemistry (total protein, albumin, total bilirubin, alanine aminotransferase, aspartate aminotransferase alkaline phosphatase, glucose, creatinine, blood urea nitrogen), electrolyte (potassium, sodium, calcium), thyroid function (thyroid function, triiodothyronine, thyroxine), coagulation function (prothrombin time, thrombin time, fibrinogen), urine routine (bacterial count, glucose, red blood cells, white blood cells), serum virological (hepatitis B virus surface antigen, hepatitis C virus antibody, syphilis specific antibody, human immunodeficiency virus antibody). During the safe follow-up period D6, retest blood routine, blood biochemistry, electrolytes, and coagulation series (note: serum virology can accept results within 28 days before screening, while other laboratory tests can accept results within 7 days before screening).
4. Chest X-Ray: if there is chest CT, it can be ignored.
5. CT/MRI/PET-CT: imaging within one month prior to screening can be acceptable at the research center or other tertiary hospitals.
6. [⁶⁸Ga]Ga-NOTA-SNA002 Administration: slowly inject [⁶⁸Ga] Ga-NOTA-SNA002 intravenously on D1 for at least 1 minute. Before injection, the subjects should drink sufficient water to ensure proper hydration, and the amount of water consumed should not be less than 500mL. After administration, regular drinking and excretion should be carried out to reduce radiation exposure.
7. Blood Sampling: collected within 30 minutes before administration, 2 minutes (± 1 minute), 5 minutes (± 1 minute), 10 minutes (± 1 minute), 30 minutes (± 2 minute), 50 minutes (± 5 minute), 100 minutes (± 5 minute), and 150 minutes (± 10 minute) after administration. Each blood sample should be tested for whole blood radiation dose within 30 minutes after collection, and centrifuged within 10 minutes after measuring whole blood radiation dose. Serum radiation dose should be tested within 5 minutes after centrifugation. After testing, the separated serum samples are divided into cryopreservation tubes, frozen (-60 °C~90 °C), and regularly sent to the central laboratory for SNA002 protein content determination.
8. Urine will be pooled for renal radiotracer clearance before drug administration, 90±30 minutes, 180±30 minutes and 300±30 minutes post injection.

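### As written, urinary excretion cannot be derived, because urine is reported per litre without void volumes; separately, the bladder source term is inconsistently specified

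*Combined protocol and SAP*

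**What the plan says.** **Urine.** The Protocol Summary (Study Design) gives the purpose: "Urine sample will be collected to evaluate the renal excretion of radioactivity before injection", and then at 90±30, 180±30 and 300±30 min. The method is: "Counts in aliquots of serum or urine will be obtained using a γ-well-type detector", and "measured activity concentrations will be converted to percentage injected activity/L". Section 7.3.3 asks only that ⁶⁸Ga in the urine samples be measured. Section 10.4.2 lists change in urine radioactivity under pharmacokinetic evaluation and gives no formula for an excreted amount. Table 4, note 8 says: "Urine will be pooled for renal radiotracer clearance before drug administration" and at the same three times, without an interval or a volume.

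**Voiding and drinking.** The Protocol Summary schedules PET/CT at 15±5, 60±10 and 120±20 min and states: "Before each imaging, the patients need to empty bladder as much as possible". Section 6.1.6 requires at least 500 mL of water before dosing and asks for repeated drinking and voiding afterwards.

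**Source organs.** The Dosimetry text in the Protocol Summary gives "i.e., brain, heart, lungs, liver, spleen, kidneys, and thyroid", without the bladder. A later paragraph there, marked as an example for information, includes urinary bladder content. Section 7.2.2 says that the fitted organs include, without limitation, "brain, chest, bladder, lungs, liver, kidneys, spleen, gastrointestinal tract, and thyroid glands", and applies a double-exponential fit to each organ. Section 6.1.7.1 reports that in monkeys the kidneys and bladder were the exceptions to low organ uptake.

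**The concern.** Activity per litre is a natural unit for blood. For urine it mixes the amount excreted with the amount of water passed, and the plan has patients drink freely. Without the volume of each void, the concentration cannot be turned into a fraction of injected activity, which is what an evaluation of renal excretion needs. If voids are also lost before or between the timed samples, the amount cannot be reconstructed later.

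The bladder matters for a second reason. It is one of the two organs that the protocol's own animal data single out, and dosimetry and biodistribution appear among the primary endpoints (Section 4.2). Yet a reader cannot tell from the three organ lists whether bladder contents are a source organ. A smooth two-exponential curve is also an awkward description of an organ that empties abruptly and is imaged only after emptying.

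**Working it through.** The plan states no urinary excretion fraction and no bladder dose, so there is no figure to reproduce. The checks below use the plan's times and its 68 min physical half-life (Section 6.1.2). Void volumes and renal half-times are assumptions, shown as ranges.

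**1. Unit.** Amount in a void (%IA) = concentration (%IA/L) × volume (L). For one reported value of 50 %IA/L:

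| Assumed void volume | Amount excreted |
|---|---|
| 100 mL | 50 × 0.1 = 5 %IA |
| 200 mL | 50 × 0.2 = 10 %IA |
| 300 mL | 50 × 0.3 = 15 %IA |
| 500 mL | 50 × 0.5 = 25 %IA |

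The same reported number covers a fivefold range in the quantity of interest.

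**2. Void times against urine windows.** The urine windows are 60-120, 150-210 and 270-330 min. Taking each pre-scan void at its scan time:

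| Void before scan at | Range (min) | Overlap with a urine window |
|---|---|---|
| 15±5 min | 10-20 | 0 of 10 min |
| 60±10 min | 50-70 | 10 of 20 min |
| 120±20 min | 100-140 | 20 of 40 min |

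Only the first void is certain to fall outside. The void comes before the scan, so on the nominal schedule the second falls just before 60 min, when the first window opens. A void inside a window is also not stated to be the one collected.

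**3. Activity that could be missed.** Assume single-exponential renal clearance with half-time T, immediate passage into the bladder and complete emptying. The share of renally cleared activity passed by time t, corrected for decay, is 1 − 0.5^(t/T):

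| T (min) | By 15 min | By 60 min |
|---|---|---|
| 30 | 29% | 75% |
| 60 | 16% | 50% |
| 90 | 11% | 37% |

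The 15 min column is the loss if only the first void is uncollected. The 60 min column applies only if the first two are both uncollected. Activity still in the bladder at 60 min is recovered at the next collected void.

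**4. Sensitivity of bladder content to voiding.** With 68 min physical decay and the bladder reset to zero at each void, time-integrated bladder activity (hours per unit of activity destined for urine) is:

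| Voids at (min) | T = 30 | T = 60 | T = 120 |
|---|---|---|---|
| 15, 60, 120, 180, 300 | 0.214 | 0.183 | 0.137 |
| 90, 180, 300 | 0.534 | 0.380 | 0.250 |
| none | 1.137 | 0.870 | 0.592 |

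The second row over the first is 0.534/0.214 = 2.5, 0.380/0.183 = 2.1 and 0.250/0.137 = 1.8. No voiding over the first row is 1.137/0.214 = 5.3, 0.870/0.183 = 4.8 and 0.592/0.137 = 4.3. The voiding assumption therefore matters, and leaving the bladder out sets its source term to zero.

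**The case against.** A reader might infer that bladder dose, and with it effective dose, will be wrong. The documents do not support that. No section makes the urine counts the input for bladder dose. Section 7.2.2 feeds organ uptake into OLINDA and names the bladder in an open-ended list. Section 10.4.4 takes organ dose from PET/CT regions of interest, and urine sits under pharmacokinetics in Section 10.4.2. Bladder content can be measured on the images. This argument stands. Its limit is that every scheduled scan follows bladder emptying and no voiding model is named, so the image route is itself under-specified.

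A reader might also infer that all the required voids are lost. Only the first is certain to miss a window, and the plan never says that pre-scan urine is discarded. Pooling in Table 4, note 8 could mean interval collection. That is possible, but the note gives no interval or volume, and even complete pooling reported per litre would not give an amount. A manual outside the documents could ask for volumes; the protocol does not.

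The organ-list conflict is partly editorial. The paragraph marked as an example looks like leftover text, and the list that omits the bladder also omits the gallbladder, for which the next paragraph draws a volume. This too stands, and it is why the remedy here is to reconcile the lists.

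Finally, urinary excretion is not itself a listed endpoint, and dosimetry appears as both primary and secondary. The primary endpoint cannot be said to fail on this ground.

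**Conclusion.** What is wrong as written is the urine excretion unit, and only that. The stated purpose is renal excretion, and %IA/L without volume cannot deliver it, whatever the true kinetics. The fivefold example rests only on assumed volumes of 100-500 mL.

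Incomplete collection is a real risk of uncertain size. About 11-29% of renally cleared activity could be missed at the first void. The 37-75% range is a worst case that needs both early voids to go uncollected and should not be read as the expected loss. Both ranges assume half-times of 30-90 min and immediate passage into urine; the documents give no human value.

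The bladder source term is inconsistently specified, and the dose result would be sensitive to how voiding is handled. That puts bladder dose at risk without showing it to be wrong. The urine correction should be made before enrolment, because volumes not recorded cannot be recovered.

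**What to change.** 1. Collect every void from injection to the 300±30 min sample, including the pre-scan voids. Record the time and volume of each, count an aliquot, and correct the count for decay to the time of injection.
2. For urine, replace %IA/L with cumulative %IA, the sum over voids of decay-corrected concentration × volume. Keep %IA/L for blood and serum. Make the Protocol Summary, Section 7.3.3, Table 4 note 8 and Section 10.4.2 say the same thing, and define pooling or remove it.
3. Reconcile the source-organ list in the Protocol Summary with Section 7.2.2 so that urinary bladder contents are included, and delete the paragraph marked as an example.
4. State how voiding is handled in the bladder time-activity estimate. The urine data may be used for this but need not be; an image-based method with a stated voiding model is also possible.

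**Cost.** Volume measurements and one or two extra aliquot counts per patient, from voids that already occur. The downside is more handling of radioactive urine containers.
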